8.5.2. Concomitant Medications and Procedures

Concomitant medications (including any medication, vitamin, herbal preparation or supplement) and procedures (defined in Section 6.7) are those received on or after the first study drug date (Day 1), including those started before Day 1 and continued after Day 1. At each study visit, participants should be questioned about any new medication or nondrug therapies or changes to concomitant medications and nondrug therapies since the last visit. Concomitant medications and nondrug therapies should be recorded in the source documents and the participant's CRF including:

- Reason for use
- Dates of administration including start and end dates
- Dosage information including dose and frequency

Any concomitant medication deemed necessary for the participant's care during the study, or for the treatment of any AE, along with any other medications, other than those listed as disallowed medications in Section 6.7.2, may be given at the discretion of the Investigator. However, it is the responsibility of the Investigator to ensure that details regarding all medications are recorded in full, in the participant's source documents and CRF.

Information regarding the use of disease-specific treatment received during the course of the study will be recorded in the source documents and the participant's CRF, including:

- For participants in the LN Cohort:
 - Additional standard of care therapy (Section 6.6) for protocol-defined Renal Flare, Severe Extrarenal SLE Flare, or Suboptimal Response
 - Treatment(s) for non-severe extrarenal SLE flare or other renal flare not defined in protocol

Vaccination and antibiotics administered for prophylaxis of meningococcal infection (if applicable) will also be recorded.

The Medical Monitor should be contacted if there are any questions regarding concomitant medications or procedures.

Allowed concomitant therapy and corticosteroid tapering for participants with LN is discussed in Section 6.5.1 and allowed concomitant therapy for participants with IgAN is discuss in Section 6.5.2.

8.6. Treatment of Overdose

For this study, any dose of ravulizumab greater than that specified in the protocol will be considered an overdose. If dose cannot be established during the Initial Evaluation Period due to blinding, suspected overdose should be defined by volume administered.

Accidental overdose or suspected overdose without any association with laboratory abnormalities or clinical symptoms should not be considered as an AE. Overdose must be reported by the Investigator within 24 hours to Alexion regardless of its association with or without an AE.

Alexion does not recommend specific treatment for an overdose.

Overdoses are medication errors that are not considered AEs unless there is an untoward medical occurrence resulting from the overdose.

In the event of an overdose or suspected overdose, the Investigator should:

- Capture and forward the event, with or without associated AEs, to Alexion Global Patient Safety via email or facsimile ([contact] or [contact]) using the Alexion Clinical Study Overdose Report Form within 24 hours of awareness.
- Contact the Medical Monitor immediately.
- Evaluate the participant to determine, in consultation with the Medical Monitor, if possible, whether study intervention should be interrupted or whether the dose should be reduced.
- Closely monitor the participant for any AE/SAE and laboratory abnormalities as medically appropriate and at least until the next scheduled follow-up.
- Obtain a plasma sample for PK analysis from the date of the last dose of study intervention if requested by the Medical Monitor (determined on a case-by-case basis).
- For unblinded participants, document the quantity of the excess dose as well as the duration of the overdose in the CRF.

Decisions regarding dose interruptions or modifications will be made by the Investigator in consultation with the Medical Monitor based on the clinical evaluation of the participant.

8.7. Pharmacokinetics and Pharmacodynamics

- Blood samples for determination of serum drug concentrations and PD assessments (free and total C5) will be collected before and after administration of study drug at the time points specified in the SoA (Section 1.3).
- Instructions for the collection and handling of biological samples will be provided by Alexion. The actual date and time (24-hour clock time) of each sample will be recorded.
- Additional information on sample collection, including blood volume requirements, is provided in the Laboratory Manual.

- The Day 1 baseline PK and PD blood samples will be collected at predose, within 90 minutes before administering study drug at visits specified in the SoA (Section 1.3). The predose blood sample may be drawn through the venous access created for the dose infusion, prior to administration of the dose.
- For all subsequent visits falling on dosing days, samples will be collected predose (within 0.5 hours prior to the start of infusion). In order to minimize needle sticks to the participant, the predose sample may be drawn through the venous access created for the dose infusion, prior to administration of the dose.
- Postdose PK and PD blood samples will be collected within 0.5 hours after completing study drug infusion. The postdose blood samples will be drawn from the participant's opposite, noninfused arm.
- For indicated visits not falling on dosing days, samples may be collected at any time that visit day.
- In the event of an unscheduled visit, PK and PD blood sample will be collected as soon as possible.
- Ravulizumab PK in urine may be conducted as an exploratory analysis based on findings from impact of proteinuria on serum PK.

Study intervention concentration information that may unblind the study will not be reported to investigative sites or blinded personnel until the study has been unblinded.

8.8. Biomarkers

Please refer to the Laboratory Study Manual for details on sample collection, including blood volume requirements. Biomarker samples may be analyzed after study completion by the absolute value and change from baseline.

8.8.1. Blood Exploratory Biomarkers

Blood (whole blood, serum & plasma) samples for biomarker research will be collected from all participants at the time points specified in the SoA (Section 1.3).

Biomarkers to be measured may include, but are not limited to, assessments of the following:

- Complement pathway dysregulation (eg, soluble C5b-9 [sC5b-9] etc)

8.8.2. Urine Exploratory Biomarkers

Urine samples for biomarker research will be collected from all participants at the time points specified in the SoA (Section 1.3).

Biomarkers to be measured may include, but are not limited to, assessments of the following:

- Complement pathway dysregulation (sC5b-9 etc)
- Renal injury biomarkers (eg, neutrophil gelatinase-associated lipocalin [N-GAL], etc)
- Creatinine

8.8.3. Kidney Biopsy Tissue Exploratory Biomarkers

Kidney tissue biopsies will be stained for the presence of biomarkers which provide clinical evidence of the disease pathophysiology and response to treatment (eg, C5b-9, etc).

For participants in the LN cohort who undergo repeated kidney biopsy(s) during the study, the LN classification will be assessed.

8.8.4. Additional Biomarker Research

Residual blood, urine, and biopsy samples from exploratory biomarkers, PK, PD, and immunogenicity, as well as residual samples from 24-hour urine collections will be stored for additional method developments of assays (eg, prognostics and/or companion diagnostics related to the study drug target, disease process, pathways associated with disease state, other complement-related diseases, and/or mechanism of action of ravulizumab).

Samples will be retained to enable further analysis on ravulizumab continues but no longer than 5 years after termination of the study or other period as per local requirements.

8.9. Other Exploratory Assessments

8.9.1. Autoantibodies (LN Cohort Only)

Blood samples will be collected for anti-dsDNA and anti-C1q) autoantibodies during Screening and according to the SoA (Section 1.3) through the end of the Extension Period (Day 351).

8.9.2. SLEDAI-2K (LN Cohort Only)

The SLEDAI-2K tool (Section 10.12) assesses disease activity across 24 disease descriptors. The total score ranges from 0 to 105, with higher scores representing more significant degrees of disease activity.

The 18 disease descriptors of the SLEDAI-2K assessment will be used for the determination of Extrarenal SLE Flare (Section 3.2.2). Extrarenal SLE Flare is defined as an increase in SLEDAI-2K ≥ 4 points that is not accounted for by the disease descriptors of proteinuria, hematuria, urinary casts, hypocomplementemia, pyuria, or an increase in anti-dsDNA antibody level. Each disease descriptor is evaluated if present at the time of the visit or within the preceding 30 days.

8.9.3. Real Time Complement Activity

Blood and urine samples will be collected (at selected study sites only) for exploratory Real Time Complement Activity (RTCA) during Screening and according to the SoA (Section 1.3) through the end of the Initial Evaluation Period (Day 183). The RTCA analysis will be performed at clinical sites using freshly collected whole blood dipotassium ethylenediaminetetraacetic acid (K2EDTA) and urine samples. Blood and urine samples for RTCA will be collected prior to administration of study drug on dosing days, if applicable. The results will be de-identified using the participant study identification number and all site personnel will be blinded from the RTCA results.

8.9.4. Participant-Reported Outcome Measures

Quality of life scales will be administered by the Investigator or a qualified site staff prior to other study procedures at visits specified in the SoA (Section 1.3).

Participants in both cohorts will have the following validated quality of life scales administered:

- The Short Form (36) (SF-36v2) Health Survey (Section 10.13) will be used to assess the participant's quality of life. In the SF-36v2 Questionnaire, participants will be instructed to rate their health and capacity to perform activities of daily living in 8 domains including physical functioning, physical role limitations, bodily pain, general health, vitality, social functioning, emotional role limitations, and mental health during the last 4 weeks. Raw domain scores will be determined and transformed to a 0 to 100 scale as described in the SF-36v2 manual. Domains get scored from 0 to 100 with lower scores indicating increased disability.
- The EuroQoL 5-Dimensions 5-Level (EQ-5D-5L) (Section 10.14) is a self-assessed, standardized instrument to measure health-related quality of life and has been used in a wide range of health conditions. The EQ-5D-5L is a 5-scale participant-reported outcome tool measuring pain/discomfort, mobility, self-care, usual activities and anxiety/depression.

Participants in the LN cohort will also have the following validated quality of life scales administered:

- The Functional Assessment of Chronic Illness Therapy (FACIT)-Fatigue scale (Section 10.15), Version 4.0, is a 13-item questionnaire that assesses self-reported fatigue and its impact upon daily activities and function over the preceding 7 days.

8.10. Immunogenicity Assessments

Antidrug antibodies to ravulizumab (ie, ADAs) will be evaluated in serum samples collected from all participants according to the SoA (Section 1.3). Additionally, serum samples should also be collected at the final visit from participants who discontinued the study drug or were withdrawn from the study. These samples will be tested by Alexion or Alexion's designee.

ADA positive samples will be further characterized for antibody titer and presence of neutralizing antibodies. Additional analyses may be performed on collected ADA samples for further analysis or characterization.

The detection and characterization of antibodies to ravulizumab will be performed using a validated assay method.

8.11. Genetics

Genetics data are not collected in this study. There are no prespecified genetic analyses in this study.

8.12. Medical Resource Utilization

Health economics/medical resource utilization and health economics parameters are not evaluated in this study.

8.13. Post-treatment Follow-up Period

During the 36-week Post-treatment Follow-up Period, participants will continue to receive standard of care and will be monitored for clinical events of interest and kidney function.

All participants will be followed for safety until 8 weeks after the participant's last dose of study drug to collect information on concomitant medications, nonpharmacological therapies and procedures, and AEs. The final safety evaluation for participants in the LN will occur at the Week 50 Visit and participants in the IgAN cohort will have a Follow-up Phone Call performed at Week 52.

Participants are not required to come into the clinic for the Post-treatment Follow-up Period visits. At each Post-treatment Follow-up Visit through Week 86, the information described below will be documented in the participant's CRF for the 12-week period since the previous study visit.

For participants in both cohorts, the following laboratory results will be documented:

- Record the UPCR results from the participant's most recent standard of care testing conducted by local laboratory. Spot urine studies may be used; a morning void is preferred.
- Record serum creatinine results from the participant's most recent standard of care testing conducted by local laboratory.

For participants in the LN cohort, information will include, but is not limited to:

- In the Investigator's opinion, did the patient experience a renal flare or extrarenal flare
- Documentation of any changes in immunosuppression therapy (intensified, new agent, or change in dose)
- Progression of kidney disease including dialysis and kidney transplant

For participants in the IgAN cohort, information will include, but is not limited to:

- Progression of kidney disease including dialysis and kidney transplant
- Documentation of any changes in immunosuppressive therapy (new agent or change in dose)
- Documentation of any changes in alternative therapy (new agent or change in dose)

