During the Initial Evaluation Period, all participants will receive a weight-based loading dose of ravulizumab or placebo on Day 1, followed by maintenance doses of ravulizumab or placebo on Day 15 and then once every 8 weeks (q8w) thereafter. Loading and maintenance doses will be determined based on body weight (see table below). All participants will receive allowed

concomitant therapy consistent with the standard of care for participants with LN and IgAN throughout the study.

During the 24-week Extension Period, participants in the LN cohort will continue to receive their randomized allocation of study drug (ravulizumab or placebo) q8w. Participants in the LN cohort will receive additional standard of care therapy in the event of a protocol-defined Renal Flare or Severe Extrarenal systemic lupus erythematosus (SLE) Flare. Approved novel treatment(s) for LN is allowed. Additional standard of care therapy for participants with Suboptimal Response is allowed at the clinical discretion of the Investigator in conversation with the Medical Monitor. For the IgAN cohort, participants in the placebo group will receive a blinded loading dose of ravulizumab at Week 26 and participants in the ravulizumab group will receive a blinded ravulizumab dose of 900 mg at Week 26. Starting Week 28, all participants in the IgAN cohort will receive open-label weight-based doses of ravulizumab q8w until the end of the Extension Period.

During the 36-week Post-treatment Follow-up Period, all participants will continue to receive standard of care and will be monitored for safety, clinical events of interest, and kidney function. Participants who discontinue study drug early and agree to remain in the study should continue to attend their scheduled protocol visits until Week 50. During these visits, all assessments except for study drug administration should be performed according to the Schedule of Assessments. Participants who withdraw from the study will be followed for safety until 8 weeks after the last dose of study drug. The end of study is defined as the last participant's last visit in the Post-treatment Follow-up Period.

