^e Participants may receive kidney biopsy (performed at the discretion of the Investigator for clinical reasons as part of standard of care). The local pathology report and microscopy slides from kidney biopsies performed at other times during the study prior to Week 86 should be sent to the Central Pathology Laboratory as soon as possible. Since examination of the biopsy pathology results may potentially unblind the study treatment (ravulizumab or placebo), Investigators and study site personnel should not examine the biopsy pathology results for immunohistochemistry of complement prior to Week 50.

^f Participants in the IgAN cohort will receive weight-based doses of ravulizumab ([Table 9](#)) q8w until the end of the Extension Period.

Abbreviations: ADA = antidrug antibody; AE = adverse event; BP = blood pressure; C3, C4 = complement components 3, 4; CH50 = 50% hemolytic complement activity; D = day; ECG = electrocardiogram; ED = early discontinuation; eGFR = estimated glomerular filtration rate; EQ-5D-5L = European Quality of Life Health 5-item questionnaire dimensions 5 level; IgAN = immunoglobulin A nephropathy; P = postdose; PD = pharmacodynamics; PK = pharmacokinetics; q8w = once every 8 weeks; SF-36 = Short Form (36) Health Survey; T = trough (predose); W = week; WOCBP = woman of childbearing potential

Table 5: Schedule of Activities During Post-Treatment Follow-up Period (Both LN and IgAN Cohorts)

Period	Post-Treatment Follow-up Period				Notes
Visit	15	16	17	18	
Week	W52 ^a (IgAN only)	W62	W74	W86/EoS	
Days and Window	D365 ± 7	D435	D519	D603	
Efficacy Assessments					
Record UPCR results (local laboratory)		X	X	X	Record local laboratory values from the participant's most recent testing prior to or on the study visit. Spot urine samples are sufficient; morning voids are preferred.
Record serum creatinine results (local laboratory)		X	X	X	Record local laboratory values from the participant's most recent testing prior to or on the study visit
Monitor for renal flare and extrarenal SLE flare (LN cohort)		X	X	X	Document in the participant's CRF for the 12-week period since the previous study visit.
Monitor for renal disease progression (IgAN cohort)		X	X	X	
Allowed concomitant therapy for LN or IgAN	Continuous monitoring				
Safety Assessments					
Concomitant medications, nonpharmacologic therapies, and procedures	X			X	Phone visit
Adverse events	X			X	Phone visit

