8.3. Safety Assessments

8.3.1. Participant Safety Card

Before the first dose of the study drug, a Participant Safety Card will be provided to participants to carry with them at all times until 8 months after the final dose of study drug. The card is provided to increase participant awareness of the risk of meningococcal infection and promote quick recognition and disclosure of any potential signs or symptoms of meningococcal infection experienced during the course of the study and to inform participants on what actions must be taken if they are experiencing signs or symptoms of infection.

At each visit throughout the study, the study staff will ensure that the participant has the Participant Safety Card.

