8.4.1. Time Period and Frequency for Collecting AE and SAE Information

All AEs (serious and nonserious) will be collected from the signing of the ICF until Week 86 or, if the participant discontinues study drug early, 8 weeks (56 days) after last dose of study drug is administered.

All SAEs will be recorded and reported to Alexion or the designee immediately and under no circumstance should this exceed 24 hours, as indicated in Section 10.3. The Investigator will submit any updated SAE data to Alexion within 24 hours of it being available.

Investigators are not obligated to actively seek AE or SAE data after conclusion of the study participation. However, if the Investigator learns of any SAE, including a death, at any time after a participant has been discharged from the study, and he/she considers the event to be reasonably related to the study drug or study participation, the Investigator must promptly notify Alexion.

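### Protocol 8.13 ends safety follow-up 8 weeks after the last dose while 8.4.1 collects AEs to Week 86, and Table 5 schedules only one AE query, at Week 86, in the 34 to 36 weeks after Week 50/52

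*Protocol*

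**What the plan says.** **Protocol 8.13** states: "All participants will be followed for safety until 8 weeks after the participant's last dose of study drug". The stated purpose includes collecting AEs. It adds that "The final safety evaluation for participants in the LN will occur at the Week 50 Visit", with a phone call at Week 52 for IgAN. Its lists of follow-up data cover local laboratory results, flares, disease progression and therapy changes. They do not name AEs, although the cohort lists are described as not exhaustive.

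**Protocol 8.4.1** states: "All AEs (serious and nonserious) will be collected from the signing of the ICF until Week 86". It applies the 8-week limit only to participants who stop study drug early.

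**The synopsis** says that during the 36-week follow-up "all participants will continue to receive standard of care and will be monitored for safety, clinical events of interest, and kidney function". Section 4.1 says the same in substance. The opening sentence of 8.13 leaves safety out.

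**Table 5 (Section 1.3)** marks adverse events and concomitant medications at Week 52 (IgAN only) and Week 86, with a phone-visit note, and leaves Weeks 62 and 74 blank in both rows. At those two visits it schedules local UPCR and creatinine results and monitoring for flare or progression, with the note "Document in the participant's CRF for the 12-week period since the previous study visit". It has no safety card row.

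**Protocol 8.3.1** has participants carry the card until 8 months after the final dose and adds: "At each visit throughout the study, the study staff will ensure that the participant has the Participant Safety Card". Table 6 lists card review at each visit among the mitigations for meningococcal infection.

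**The concern.** For a participant who completes treatment, 8.13 and 8.4.1 cannot both govern. A site that relies on 8.13 could close AE collection at Week 50 or 52. A site that relies on 8.4.1 and Table 5 would ask once, by phone, about the preceding 34 to 36 weeks. Late infections, including the only AE of special interest (meningococcal infection, 8.4.6), could then be ascertained differently between sites and recalled late.

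The look-back adds to this. The other follow-up items in 8.13 and Table 5 cover the 12 weeks since the previous visit. If a site carried that look-back over to the Week 86 AE call, events between Week 50/52 and Week 74 would never be asked about.

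The analysis expects these data. Protocol 9.4 and SAP 5.6 present safety separately for the Post-treatment Follow-up Period, and SAP 5.6.2 lists post-treatment AEs by participant. An empty listing could not be told apart from AEs that were never collected.

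**Working it through.** **Inputs (Protocol Section 1.3)**
- Last scheduled dose: LN Day 295 (Week 42, Table 3); IgAN Day 309 (Week 44, Table 4).
- Follow-up visits (Table 5): Week 52 = Day 365, Week 62 = Day 435, Week 74 = Day 519, Week 86 = Day 603. The Week 50 Visit is Day 351.
- Safety card period: 8 months after the final dose (8.3.1). The protocol does not convert this to days. I assume 8 × 365.25/12 = 243.5, taken as 243, and check 224 days (8 × 28) and 248 days (8 × 31).

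**Step 1: reproduce the plan's own dates.** Last dose + 56 days:
- LN: 295 + 56 = Day 351 (Week 50).
- IgAN: 309 + 56 = Day 365 (Week 52).

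Both match 8.13. Week 50 + 36 weeks = Week 86, which matches the end date in 8.4.1 and Table 5.

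**Step 2: interval from the last on-schedule AE query to the next**
- LN: 603 − 351 = 252 days (36 weeks).
- IgAN: 603 − 365 = 238 days (34 weeks).

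**Step 3: share of the card period without a scheduled AE query**

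| | LN | IgAN |
|---|---|---|
| Card period ends | 295 + 243 = Day 538 (about Week 77) | 309 + 243 = Day 552 (about Week 79) |
| Last AE query inside it | Day 351 | Day 365 |
| Days without a query | 538 − 351 = 187 | 552 − 365 = 187 |
| Share of 243 days | 77% | 77% |
| Week 86 falls after the period by | 603 − 538 = 65 days | 603 − 552 = 51 days |

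Range: (224 − 56)/224 = 75%; (248 − 56)/248 = 77%. The length assumed for a month hardly matters.

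**Step 4: effect of asking at Weeks 62 and 74**
- LN intervals: 435 − 351 = 84; 519 − 435 = 84; 603 − 519 = 84 days.
- IgAN intervals: 435 − 365 = 70; then 84 and 84 days.
- Timing after last dose: LN Days 140 and 224; IgAN Days 126 and 210. All fall within 243 days. With 28-day months, the LN Week 74 query falls on the last day of the period.

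**The case against.** Much of the case on the other side stands.

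- **A reader might infer that Table 5 follows neither section.** It does not support that. Section 8.4.1 sets a collection period, not a query frequency, and the Week 86 call closes that period. On the end date, Table 5 sides with 8.4.1.
- **A reader might infer that there is no safety contact for 8 months.** That is too strong. Flares, therapy changes, dialysis and transplant are recorded at Weeks 62 and 74. Serious events that a site learns of are reportable within 24 hours. What is missing is a scheduled AE query.
- **A reader might infer that participants lose the card reminder.** The text of 8.3.1 and Table 6 already requires the check at each visit, and Weeks 62 and 74 are numbered visits (16 and 17). What is missing is the row that would prompt it.
- **A reader might treat 8 months as a defined AE risk window for all of the approximately 120 participants.** The documents attach 8 months to the card and to contraception; their treatment-emergent window is 56 days. About 20 LN placebo participants never receive ravulizumab, so about 100 (40 LN, plus 60 IgAN after the Week 26 switch) are planned to be exposed. The schedule gap applies to all 120, but drug-related risk does not.
- **Planned TEAE summaries do not change.** A query falls exactly 56 days after the last scheduled dose in both cohorts, and SAP 5.6.2 places later events in listings only.

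It is also fair that no passage requires a query every 12 weeks, so the interim queries are a recommendation rather than the correction of an error. None of this removes the conflict between 8.13 and 8.4.1 or the missing card row.

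**Conclusion.** The point holds in a bounded form. Section 8.13 conflicts with 8.4.1, the synopsis and Table 5 on when AE collection ends for participants who complete treatment. After Week 50/52 one AE query is scheduled, 252 days (LN) or 238 days (IgAN) later, and it falls after the card period has closed. About 77% of that period (75% to 77% across month lengths) has no scheduled AE query, and Table 5 omits the required card check.

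These figures assume doses and visits on their nominal days. They describe the schedule of queries, not events known to be missed. The primary endpoint and the TEAE tables are untouched; the effect is on the completeness and comparability of late safety data. The change is worth making because it is cheap.

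**What to change.** 1. **Reconcile 8.13 with 8.4.1 and Table 5** so that AE collection runs to Week 86 for participants who complete treatment, and name AEs among the follow-up data in 8.13. Keep the 8-week limit for early discontinuation of study drug (8.4.1) and for withdrawal (4.1, 7.2), and keep the IgAN Week 52 call. A blanket replacement of the 8-week text would create new conflicts with those sections.
2. **Add a safety card review row to Table 5** for the follow-up visits, to match 8.3.1 and Table 6.
3. **Add AE and concomitant medication queries at Weeks 62 and 74** for both cohorts. The longest interval between AE queries falls from 252 or 238 days to 84.

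**Cost:** amendment wording and, possibly, two short phone calls per participant. Section 8.13 does not require clinic attendance at these visits and the laboratory values come from routine care, so direct contact cannot be assumed. No new visits or samples are needed.
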